Descriptive statistics were calculated for each variable. The normality of the distribution of data was verified by the Shapiro-Wilk test. Variables showing skewed distributions were log-transformed to obtain a normal distribution. Relative changes within each group were assessed using a paired Student's t test. To compare baseline variables the Student's t test, standardized differences ($\pm 90\%$ confidence level) and qualitative differences were estimated. To detect between-group differences, multiple 2 x 2 (group x time) mixed-analysis of variance was performed and adjustments for multiple comparisons were made using the Bonferroni method by dividing the significance level of 0.050 by the number of comparisons, additionally standardized differences ($\pm 90\%$ CL) and qualitative differences were estimated. The effect size of standardized differences was determined by Cohen's d statistic, and the Hopkins' scale was used to determine the magnitude of the effect size, where 0 to 0.19 = trivial, 0.20 to 0.59 = small, 0.60 to 1.19 = moderate, 1.2 to 1.99 = large, and >2 = very large (Hopkins et al 2009). A practically worthwhile difference was assumed when the difference score was ≥ 0.2 of the between-subject SD. Qualitative assessment indicates the likelihood for the between-group differences to be substantial, referring to possible differences, to likely, to very likely, and to almost certain differences. The probability of a true difference between groups was qualitatively classified as almost certainly not: $<0.5\%$; very unlikely: 0.5% to 5%; unlikely: 5% to 25%; possible: 25% to 75%; likely: 75% to 95%; very likely: 95% to 99.5%; and almost certain: $>99.5\%$. A substantial effect was defined as $>75\%$ (Batterham and Hopkins 2006).

Functional tests

30-second chair stand test

Objectives: (Test No. 1)

1-To assess the strength of the extensor muscles of the knees and hips, responsible for gait failure and falls in 30 seconds.

2-To evaluate the resistance to loss of lower body strength, which causes early fatigue, in 30 seconds.

3- To evaluate the perceived effort and relative intensity of the patient's effort.

Bibliographic references. Validity and standardization

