- Wednesday: Familiarization 1 and functional tests nº 1,2 and 3
- Friday: Familiarization 2 and functional test nº 4

Week 2

- Monday: Familiarization 2 (material and training)
- Friday: Familiarization 2 (material and training)

Week 3 to week 12 (intervention period)

- Tuesday: Intervention period Intervention
- Friday: Intervention period

Week 13 Final evaluation.

- Monday: Post-intervention blood sampling, disease impact questionnaires
- Wednesday: Familiarization 1 and functional tests 1, 2 and 3.
- Friday: Functional test nº 4

Participants' arms.

Participants were divided into 2 non-randomized groups with a total of 37 participants at baseline and overcoming the different phases of exclusion 13.

- **Intervention group:** This group will perform each of the above research stages and perform the occlusive cuff intervention period. n= 7 participants.
- **Non-intervention group:** This group will perform each of the above research stages and will perform the intervention period without the occlusive cuff. n= 6 participants.

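### Cohen's d without a stated small-sample correction overstates between-group and baseline differences by about 7.5% on average with 7 and 6 participants, a small and easily removed bias in the number that the plan classifies

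*Combined protocol and SAP*

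**What the plan says.** All references are to the combined protocol and SAP.

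- **Effect size** (Statistical analysis): "The effect size of standardized differences was determined by Cohen's d statistic". No small-sample correction is mentioned anywhere, and the SD used as divisor is not defined beyond a reference to the between-subject SD.
- **Grading** (same section): the scale is "0 to 0.19 = trivial, 0.20 to 0.59 = small, 0.60 to 1.19 = moderate, 1.2 to 1.99 = large, and >2 = very large".
- **Threshold** (same section): "A practically worthwhile difference was assumed when the difference score was ≥ 0.2 of the between-subject SD".
- **Where standardised differences apply** (same section): they are named for the baseline comparison and for the between-group comparison. Change within a group is assigned a paired t test. No within-group d is prescribed.
- **Numbers** (Participants' arms): "Participants were divided into 2 non-randomized groups with a total of 37 participants at baseline and overcoming the different phases of exclusion 13". The cuff group has "n= 7 participants" and the group walking without the cuff has "n= 6 participants".

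**The concern.** Cohen's d divides a mean difference by an estimated SD. With few degrees of freedom, the reciprocal of that SD is on average too large, so d is biased away from zero. In a large trial this can be ignored. Here there are 11 degrees of freedom, and the plan converts d into verbal classes with hard boundaries and reads differences against a 0.2 SD rule. A known, removable bias therefore sits in the figure behind the reported labels. Some outcomes near a boundary would be placed one class higher than a corrected estimate would place them.

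**Working it through.** **The plan's own figure.** No effect size, SD or power is stated for the between-group comparison, so there is no figure for d to reproduce. The one computable design figure is the sample size of 75: 1.96² × 0.018 × 0.982 / 0.03² = 75.4. It reproduces, but it concerns the precision of a prevalence and has no bearing on d.

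**Inputs.** n = 7 and n = 6 (Participants' arms); cut-offs 0.2, 0.6, 1.2 and 2 and the 0.2 SD rule (Statistical analysis). Assumptions: normal data, equal variances, and an SD pooled over both groups, so df = 7 + 6 − 2 = 11.

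**Step 1: the bias factor.** The mean of d is the true effect divided by J, where J(df) = Γ(df/2) / [√(df/2) · Γ((df−1)/2)].

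- J(11) = 0.930, so mean inflation is 1/0.930 − 1 = 7.5%.
- The usual approximation agrees: 1 − 3/(4 × 11 − 1) = 0.930.
- If one SD over all 13 participants were used (df = 12), the inflation would be 6.8%.

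**Step 2: shifted boundaries.** The uncorrected d that corresponds to each cut-off after correction is the cut-off divided by J(11):

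| Cut-off | Uncorrected d needed |
|---|---|
| 0.2 | 0.215 |
| 0.6 | 0.645 |
| 1.2 | 1.290 |
| 2.0 | 2.151 |

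An observed |d| between the two columns falls one class.

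**Step 3: simulation** (400,000 trials of 7 v 6 per row; g = 0.930 × d):

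| True effect | Mean d | Mean g | SD of d | Class changes | Reaches 0.2: d | Reaches 0.2: g |
|---|---|---|---|---|---|---|
| 0 | −0.002 | −0.002 | 0.614 | 6.7% | 72.5% | 70.6% |
| 0.2 | 0.216 | 0.201 | 0.616 | 7.0% | 74.2% | 72.3% |
| 0.5 | 0.538 | 0.501 | 0.630 | 8.1% | 81.3% | 80.0% |
| 0.6 | 0.646 | 0.600 | 0.636 | 8.7% | 84.2% | 83.0% |
| 1.2 | 1.290 | 1.200 | 0.687 | 11.5% | 97.0% | 96.8% |

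The chance that the absolute value reaches 0.2 falls by at most about 2 percentage points.

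**Step 4: size against imprecision.** The expected bias is 0.2 × 0.075 = 0.015 at a true effect of 0.2, 0.045 at 0.6 and 0.09 at 1.2. At zero effect, the standard error of d (leaving out uncertainty in the SD) is √(1/7 + 1/6) = 0.556, and the 90% half-width is about 1.0.

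**Step 5: is g the better estimate?** Var(d) = (11/9)(1/7 + 1/6 + δ²) − (δ/J)². At δ = 0.5 this is 0.6839 − 0.2891 = 0.3948, so the SD is 0.628. Root mean squared error is √(0.3948 + 0.0377²) = 0.63 for d, and 0.930 × 0.628 = 0.58 for g. The correction removes the bias and also reduces the error.

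**The case against.** The strongest objection is proportion. A bias of 0.015 to 0.09 is minor when the sampling SD is 0.6-0.7. The 7.5% is a mean pulled up by the right tail: the median inflation at 11 df is 3.1%, and in simulation the observed d lies below the true value in 48-50% of results. Changing a class is also not the same as getting it right. The share of results placed in the true class moves from 40.9% to 42.4% at a true effect of 0.2 and from 34.6% to 36.6% at 0.5, but falls from 37.9% to 35.8% at 1.2. Most misclassification comes from imprecision and remains after correction. All of this stands, and it limits the point to a refinement.

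It can also be said that the absence of a correction is inferred from silence. That is so, but the plan names Cohen's d and nothing else. One sentence would settle it.

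Two stronger readings are tempting and are not supported:

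- **A within-group inflation of 15-19%.** This is the arithmetic for a d standardised on one group's own SD: J(6) = 0.869, or 15%, for n = 7, and J(5) = 0.841, or 19%, for n = 6. The plan assigns a paired t test to within-group change and prescribes no within-group d. If one were reported, the figure would depend on its divisor. With the average of the pre and post SDs it is 7-11% (n = 7) or 9-14% (n = 6), for assumed pre-post correlations of 0 to 0.8. With the SD pooled over both groups it is 7.5%.
- **A bias that flatters the programme.** The inflation is multiplicative. It enlarges a difference in favour of the no-cuff group, or a baseline imbalance, just as much, and it vanishes when the true effect is zero.

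**Conclusion.** The point holds as a minor one. As written, the plan grades an effect size that overstates the absolute size of a non-zero between-group or baseline difference by 7.5% on average. About 7-12% of results would carry a different label after correction, always one that is lower in absolute size. This rests on normality, on an SD pooled over both groups, on 7 and 6 being the numbers analysed, and on no correction being applied in practice.

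The documents do not support saying that each observed d is too large, that the bias favours the cuff, or that conclusions would change materially. The correction would do nothing for the width of the intervals, which dominates the uncertainty.

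**What to change.** In the Statistical analysis section:

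1. Name the standardiser and its degrees of freedom, for example the SD pooled over both groups (11 df).
2. Replace Cohen's d with Hedges' g (d multiplied by J at those degrees of freedom) for the baseline and between-group standardised differences.
3. Apply the Hopkins scale and the 0.2 threshold to g.
4. State how the 90% limits are computed, using a method suited to g. If they are exact noncentral-t limits, do not multiply them by J. They already target the true standardised effect, and rescaling would spoil their coverage.
5. If a within-group d is also reported, name its standardiser and use J at that SD's degrees of freedom. The inflation to be removed is about 7-19%, depending on the choice.

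The cost is one multiplication per effect size and a few sentences of text, with no new data. The downside is that stated effects become slightly smaller.

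### The likelihood scale has no inconclusive class and leaves direction and reference SD unstated; at 7 v 6, 74–81% of null results fit both a worthwhile gain and a worthwhile loss, yet get a definite word (pre-post correlation 0.5–0.8 assumed)

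*Combined protocol and SAP*

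**What the plan says.** The Statistical analysis section compares the groups by a group-by-time mixed ANOVA with Bonferroni adjustment. It adds standardized differences with 90% limits and a qualitative likelihood.

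- **Threshold:** "A practically worthwhile difference was assumed when the difference score was ≥ 0.2 of the between-subject SD". It does not say whether this SD is that of baseline values or of changes.
- **What is graded:** "Qualitative assessment indicates the likelihood for the between-group differences to be substantial". No direction is named.
- **Scale:** it opens "The probability of a true difference between groups was qualitatively classified as almost certainly not", and this lowest class is under 0.5%. The next are "very unlikely: 0.5% to 5%; unlikely: 5% to 25%; possible: 25% to 75%; likely: 75% to 95" (per cent), followed by two classes above that. None is called unclear or inconclusive, and no rule covers limits that span both directions. A probability above 75% counts as a substantial effect.
- **Size:** under Participants' arms, "Participants were divided into 2 non-randomized groups", with "n= 7 participants" in the cuff group and "n= 6 participants" in the group without the cuff.

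**The concern.** Only the three classes below 25% report that a difference is improbable. With 13 people the interval around any difference is wide. A probability computed from a wide interval centred near zero lands in the middle of the scale because little is known, not because a difference is moderately likely. With no inconclusive class, the reader cannot tell these two situations apart.

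This matters most where absence of a difference is the expected result. Hypothesis 5 predicts that TAS, MDA, liver enzymes, biochemistry and hemogram stay stable, and hypothesis 6 claims safety. If the scale seldom says 'unlikely', or says it on uninformative data, it cannot serve those hypotheses. Uninformative results can also pass the >75% rule and be reported as substantial.

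**Working it through.** The plan states no operating figure for this scale, so there is none to reproduce. Its n = 75 does reproduce (1.96² × 0.018 × 0.982 / 0.03² = 75.4), but it comes from the precision of a prevalence and has no bearing on this comparison.

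**Inputs.** From the plan: groups of 7 and 6, hence 7 + 6 − 2 = 11 df; threshold 0.2 SD; class limits at 25% and 75%; 90% limits. Assumed: pre-post correlation r of 0.5–0.8, with 0.9 as a sensitivity value; baseline SD as reference; the usual flat-prior t calculation.

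**Standard error.** With two time points, group-by-time is a comparison of mean changes. In units of the baseline SD:

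SE = √(2(1 − r)) × √(1/7 + 1/6), where √(1/7 + 1/6) = 0.556.

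- r = 0.5: SE = 1.000 × 0.556 = 0.556
- r = 0.8: SE = 0.632 × 0.556 = 0.352

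**Probability at an observed difference of exactly zero, taking the expected SD.**

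- One direction, P(T₁₁ > 0.2/SE): 0.363 (r 0.5), 0.291 (r 0.8)
- Either direction, twice that: 0.726 and 0.581

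All four exceed 25%. They fall below it only when r exceeds about 0.87 (one direction) or 0.956 (either direction).

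**Simulated null trials** (200,000 per r, normal data, SDs estimated from each sample). Three readings of the probability are possible: either direction, the observed (larger) direction, or fixed as 'cuff better'.

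| Share of null results | r = 0.5 | r = 0.8 | r = 0.9 |
|---|---|---|---|
| Below 25%, either direction | 0% | 0.1% | 2% |
| Below 25%, observed direction | 0.04% | 2% | 12% |
| Below 25%, fixed direction | 37% | 45% | 54% |
| 90% limits include both +0.2 and −0.2 SD | 81% | 74% | 63% |
| Above 75%, either direction | 73% | 36% | 19% |
| Above 75%, observed direction | 31% | 22% | 15% |
| Above 75%, fixed direction | 16% | 11% | 8% |

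The row on the 90% limits does not depend on the reading. Of the fixed-direction results below 25%, 75% (r 0.5) to 71% (r 0.8) have limits that include both thresholds.

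**Effect of an 'unclear' rule.** Removing results whose 90% limits include both thresholds changes the share of null results called substantial as follows (r 0.5, then r 0.8):

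- either direction: 73% and 36% become 19% and 21%
- observed direction: 31% and 22% become 18% and 19%
- fixed direction: 16% and 11% become 9% and 10%

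**If 0.2 refers to the SD of change,** then at any r all null results are 'possible' or stronger on the first two readings, and 63% on the fixed-direction reading.

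**The case against.** The strongest reply has four parts.

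1. **The low classes are not out of reach.** A reader might infer from the zero-difference figures that the lower half of the scale cannot occur. The documents do not support that. They give no pre-post correlation, SDs are estimated from 13 people, and at r = 0.9 the low classes take 2–12% of null results on the non-directional readings. The hypotheses are partly directional (a positive impact is expected), so 'cuff better' is a tenable reading, and then more than a third of null results fall below 25%. This part stands.
2. **'Possible' is not support for the cuff.** A reader might infer that uninformative data become weak evidence in its favour. On the readings that give 98–100%, the grade has no fixed direction, and by symmetry about half of null differences favour the group without the cuff. This part also stands.
3. **'Possible' is not a positive finding,** since the plan's rule is >75%. That is true, but the plan reports possible differences as a grade, and null results do exceed 75%, in 11–73% of cases across readings at r 0.5–0.8.
4. **Other output exists:** the ANOVA, the 90% limits, and Cohen's d with a 'trivial' band. A careful author could report a null result properly from these. They soften the problem but do not correct the likelihood word printed beside them.

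Fixing a direction does not rescue the scale. Most of its 'unlikely' results are as uninformative as the 'possible' ones, so the error then runs against the cuff.

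**Conclusion.** The concern holds in a conditional form. The plan leaves open the direction, the reference SD and the treatment of inconclusive data. At 7 v 6 with r of 0.5–0.8 and a baseline-SD threshold, 74–81% of null results are compatible with both a worthwhile gain and a worthwhile loss, yet each receives a definite word on any reading.

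The 98–100% figure for 'possible' or stronger applies only to the either-direction and observed-direction readings over that range of r. The either-direction reading is the most literal one. The documents do not support saying that the low classes cannot be reached, that every outcome is affected, or that the scale favours the cuff.

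All frequencies rest on the assumed r, normal data and no true effect. They do not address bias from non-random allocation.

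**What to change.** In the Statistical analysis section:

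1. State whether the likelihood covers either direction, the observed direction or a fixed one, and which SD (baseline or change) defines the 0.2 threshold.
2. Report three probabilities for each between-group difference: favours cuff, within ±0.2 SD, favours no cuff.
3. Label a result 'unclear' whenever the planned 90% limits include both +0.2 SD and −0.2 SD.
4. Apply the seven likelihood words and the >75% 'substantial' rule only to results that are not unclear.

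The plan should not add a statement that the low classes are not expected to occur, because that depends on the reading and on r.

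**Cost:** a change of wording and one rule applied to limits already planned; no new data. Most outcomes will be labelled 'unclear'. The rule is also not a full cure: about 18–21% of null results (9–10% with a fixed direction) would still be called substantial.

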1- The training program has a positive impact on quality of life and functional autonomy in people with fibromyalgia.

2- The training program is effective and generates little fatigue.

3- The training program has a high adherence in people with fibromyalgia.

4- The hypoxia produced and the relative intensity of the program has a direct impact on the balance of oxidant/antioxidant levels.

5- The levels of TAS, MDA, liver enzymes, biochemical variables and hemogram remain stable without significant alterations.

6- Occlusive training in people with fibromyalgia proves to be an effective and safe therapy as part of the treatment.

Objectives

Main Objective

To improve the quality of life and functional autonomy.

Specific Objectives

- 1- To achieve results by minimizing the fatigue produced in people with fibromyalgia.

- 2- To get people accustomed to the adapted program and make it part of their routine.

- 3- To measure variables in blood/plasma to verify the results obtained for a better understanding of the disease and its impact.

- 4- To identify those blood/plasma variables most susceptible to occlusive training that will allow a better understanding of fibromyalgia disease.

- 5- To test the effectiveness and adherence of occlusive training in people with fibromyalgia by means of blood/plasma samples, functional tests and questionnaires.

- 6- To evaluate occlusive training as a valid physical complementary therapy for people with fibromyalgia.

Methodology

The methodology will be carried out by an experimental design research to test the effect of the independent variable on the dependent variable. In this case, the independent variable will be the pressure exerted by the occlusive cuff on the thigh musculature during the planning of aerobic exercise walking of low intensity and reduced time, and its impact on the dependent variable, which is determined by plasma and blood values, mitochondrial protein expression, standardized questionnaires of the impact of the disease (psychometric), and functional tests of physical condition (distances and times performed), which will be measured before and after the intervention period.

Study population

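### Two unranked criteria judge the same between-group difference, and the unadjusted >75% rule labels about 22–31% of null outcomes substantial at 7 vs 6

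*Combined protocol and SAP*

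**What the plan says.** In the Statistical analysis section, between-group differences are to be detected with a 2 x 2 (group by time) mixed ANOVA for each variable, and "adjustments for multiple comparisons were made using the Bonferroni method by dividing the significance level of 0.050 by the number of comparisons". The same sentence continues with "additionally standardized differences" at a 90% confidence level, together with qualitative differences. The paragraph then sets a practically worthwhile difference at 0.2 of the between-subject SD. It explains that "Qualitative assessment indicates the likelihood for the between-group differences to be substantial", lists probability bands, and closes with a cut-off: "A substantial effect was defined as" a probability above 75%.

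The number of comparisons is not given. Bonferroni is applied only to the significance level. No sentence ranks the two criteria or calls the second descriptive, and none fixes its direction or provides an 'unclear' outcome.

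Under Participants' arms, the plan states that "Participants were divided into 2 non-randomized groups with a total of 37 participants at baseline". After exclusions, 13 remained: 7 in the cuff group and 6 in the group without the cuff. The first hypothesis is that "The training program has a positive impact on quality of life and functional autonomy in people with fibromyalgia", and the main objective is "To improve the quality of life and functional autonomy". Neither is tied to one of the two criteria.

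**The concern.** The two criteria can give opposite answers for the same outcome, and the plan does not say which prevails. The Bonferroni test is strict, and at 13 participants most outcomes will probably miss it. The >75% rule is lenient and is applied to every outcome without adjustment. If an outcome fails the first and passes the second, the report may call the effect substantial on the plan's own definition. Nothing in the text stops that label from being read as support for the hypotheses of positive impact and effective therapy. What is at stake is which results count as evidence for the cuff.

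**Working it through.** **The plan's own figure.** The plan gives no error rate for either criterion. Its only design figure is n = 75 (Sample size), from 1.8% prevalence, 95% confidence and ±3% precision: 1.96² × 0.018 × 0.982 / 0.03² = 75.4. This reproduces, but it is a precision calculation for one prevalence and has no bearing on a between-group comparison.

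**Inputs from the documents.** Group sizes 7 and 6, so 11 degrees of freedom; worthwhile difference 0.2 between-subject SD; cut-off 75%; significance level 0.05 divided by the number of comparisons, k.

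**Assumptions.** No true effect, comparable groups, normal data, equal variances. The pre-post correlation r is not in the documents, so a range is shown. The probability is taken from the t distribution of the difference in change scores, and each direction is judged separately.

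**Per-outcome rate, closed form.** In between-subject SD units, SE = √(2(1−r)) × √(1/7 + 1/6) = √(2(1−r)) × 0.556. The rule fires when |t| > t(0.75; 11) + 0.2/SE, with t(0.75; 11) = 0.697.

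| r | SE | 0.2/SE | critical \|t\| | smallest difference that fires (SD) | null rate, either direction |
|---|---|---|---|---|---|
| 0.5 | 0.556 | 0.359 | 1.057 | 0.59 | 31.3% |
| 0.7 | 0.431 | 0.464 | 1.162 | 0.50 | 27.0% |
| 0.8 | 0.352 | 0.568 | 1.266 | 0.45 | 23.2% |

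The last column is also the two-sided p-value at which the label is first earned: about 0.31 at r = 0.5 and 0.23 at r = 0.8.

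**Per-outcome rate, simulated with SDs estimated from the data** (200,000 trials per r at 7 vs 6; 100,000 at 38 vs 37).

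| Condition | r = 0.5 | r = 0.7 | r = 0.8 |
|---|---|---|---|
| Either direction | 30.8% | 26.4% | 22.3% |
| False benefit only | 15.4% | 13.1% | 11.1% |
| Either direction, with an unstated 'unclear' filter (dropped if both directions exceed 5%) | 18.3% | 19.8% | 19.3% |
| Either direction, n = 75 split 38 vs 37 (split assumed) | 12.5% | 7.5% | 4.3% |

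A separate simulation of 300,000 trials gave 31.0%, 26.5% and 22.5% for the first row. Outside this range of r, the first-row rate is 36% at r = 0, 15% at r = 0.9 and 8% at r = 0.95. In the same simulations an ordinary t test at 0.05 rejects in about 5%, as it should.

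**Against Bonferroni.** The Definition of variables section names 4 questionnaires and 5 fitness tests, so take k = 9: 0.05/9 = 0.0056. Then 0.223/0.0056 ≈ 40 and 0.308/0.0056 ≈ 55. With the filter the ratio is 33 to 36. Blood and plasma values and the modified shuttle walk would increase k. Under the null, about 97–98% of the false labels fail the test at 0.05/9.

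**At least one false label among 9 outcomes** (40,000 trials, equal correlation between outcomes, 7 vs 6).

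| Between-outcome correlation | r = 0.5 | r = 0.7 | r = 0.8 |
|---|---|---|---|
| 0 | 96% | 94% | 90% |
| 0.5 | 90% | 84% | 78% |
| 0.7 | 79% | 72% | 65% |
| 0.5, benefit only | 52% | 47% | 42% |

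The independence row can be checked directly: 1 − (1 − 0.308)⁹ = 96%. Under Bonferroni the corresponding family rate is 3–5%.

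**The case against.** The strongest reply is that the paragraph separates the criteria by purpose: the ANOVA is there to detect differences, and the standardized and qualitative differences are estimated in addition. On that reading the >75% label is description, and the plan lacks only a clarifying sentence. The reading is possible, but it is implicit. A formal definition with a cut-off is decision language, and no sentence limits its use.

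Several points of emphasis do stand:
- The stated harm is a false claim of benefit, and the rate that matches it is 11–15%, about half the either-direction rate.
- If the cited method brings an 'unclear' rule with it, which the documents cannot settle, the either-direction rate is 18–20%, and 9–10% for benefit only.
- The ratio of 40–55 combines a lenient threshold with missing multiplicity adjustment, and rests on a count of nine that the plan does not state. Against an unadjusted 5% test the ratio is about 4 to 6.
- The correlation r is assumed, and the rate falls to 8% at r = 0.95.
- Allocation was not randomized, so comparable groups is itself an assumption, and any selection bias comes on top.

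None of these brings the rule near the error rate that the plan sets for its own adjusted test.

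**Conclusion.** The concern holds. As written, the plan lets an outcome fail its multiplicity-adjusted test and still meet its definition of a substantial effect. Under the null at 7 vs 6, nearly all such labels would contradict the adjusted test. The rule fires in about 22–31% of null outcomes for r from 0.8 to 0.5 in either direction, and 11–15% for benefit only. Across nine outcomes, at least one false label is more likely than not at every either-direction setting tabulated. The exact rates depend on the assumed r, between-outcome correlation and k; the missing precedence does not. This is a faulty decision rule and must be corrected before conclusions are drawn. Correcting it does not remove the wider limits of 13 non-randomized participants.

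**What to change.** Reword the Statistical analysis paragraph as follows:
- State that only the Bonferroni-adjusted group-by-time test supports a claim of a cuff effect. Give k and list the outcomes it counts.
- Remove the >75% definition and the probability labels as a basis for conclusions.
- Keep Cohen's d and intervals as description, with intervals at the level that matches the test (for k = 9, 1 − 0.05/9 = 99.4%).

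An optional further step applies only if no outcome data have been analysed: name one outcome for each half of the main objective, for example FIQ and 6-minute walk distance. Test each at 0.025 with 97.5% intervals and label the rest exploratory. The Statistical analysis and Participants' arms sections are partly in the past tense, so if data have been seen, either disclose that choice as post hoc or keep Bonferroni over all listed outcomes.

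The cost is one paragraph and no new data, plus revision of any results text already written with the labels. There will be fewer positive statements, and most outcomes will be inconclusive. At 80% power (two-sided, 11 degrees of freedom) the detectable difference at 7 vs 6 is 2.45 SD of the change score for k = 9, or 1.94 SD with two outcomes at 0.025.
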